Assessment of BHB Concentration Agreement Among Sampling Locations and the Impact of Ketosis on Erythropoietin Levels: A Two-Part Study

Aim and perspective

This study's main goal (part 1) is to determine

- i. agreement in beta-hydroxybutyrate (BHB) of capillary and venous blood estimates and subsequently whether agreement is dependent on BHB level, and
- ii. agreement in BHB of finger and earlobe capillary samples, and
- iii. agreement in BHB of venous estimates (estimated by point-of-care device) and full blood (estimated by use of hydrophilic interaction liquid chromatography tandem mass spectrometry (HLCMS))

The main goal (part 2) is to determine

- i. effects of ketosis on erythropoietin(EPO) short-term and long-term
- ii. derived effects on erythropoiesis and iron metabolism from two-week intermittent ketosis

This study will establish (part 1) whether it is appropriate to select a specific sampling site for measuring BHB in patients and performing research, and whether there is a difference between measurements capillary and venous blood. The agreement between the KetoSure, a point-of-care-test (POCT) device, and the gold standard will also be examined, offering insight into any discrepancies with point-of-care estimates obtained by electrochemical estimations and HLCMS. High BHB measurement validity is required in both clinical and experimental contexts. First, BHB quantification may aid in clinical decision-making for suspected hyperinsulinemia, hypoglycemia of uncertain etiology, diabetic ketoacidosis, and other diseases. Second, a substantial amount of research has been conducted on BHB inference and ketones in general in recent years, and the validity of the interpretation of these studies is highly dependent on measurement precision in regards to which sample type and sampling site is applied.

In addition, the effects of ketosis on EPO concentrations will be investigated (part 2) from blood samples obtained during part 1 (acute effects) and at day 7 and day 14 where participants are intermittently ketotic allowing also for investigations on EPO-derived effects on erythropoiesis and iron metabolism.

Background

During an experiment in which samples were obtained from two distinct places, namely the finger pulp and the earlobe, the KetoSure ketonometer disclosed a discrepancy in BHB estimates, prompting us to review the relevant literature on discrepancy between sampling sites.

In glucose determination, such discrepancy between capillary and venous blood concentration is well-known[1]. In contrast to our incidental findings, capillary glucose estimations are higher than venous plasma estimates. Several hypotheses, with variances in hematocrit being the most prevalent, have been suggested as explanations for these discrepancies; however, conclusions change depending on the analyte of interest[2]. In addition to the comparator, the POCT detection method, kind of enzymatic reaction, and pH value are of utmost importance[3].

As reported in a 2016 study, the accuracy of capillary BHB measurement has been tested in various contexts and with various ketonometers[4]. Primarily with the intent of improving its ability to identify diabetic ketoacidosis. Similarly, the accuracy of glucose estimates from different capillary sample sites has varied in response to both glucose concentration and capillary sampling site[5].

To our knowledge, neither the agreement between venous blood and full blood+HLCMS values nor the disparity between different sampling sites for the extraction of capillary samples have been investigated.

Two investigations have indicated a link between ketosis and EPO[6,7]. Both, however, had other primary endpoints, and thus were not meant to answer this particular research question. In addition, only the correlation between ketosis and EPO levels has been studied. Thus, erythropoietic effects of EPO in the bone marrow (and elsewhere) have not been studied. The incorporation of ambulatory blood testing, and the extension of the ketosis, such effects can be investigated over an appropriate time frame and provide the opportunity to investigate not only the relationship between exogenous ketosis in general, but also any temporal aspects thereof, as the study design includes both an "acute" (part 1) and a "chronic" (part 2) factor.

References

The study day duration will be approximately four hours with participants reporting in at Klinik for Diabetes & Hormonsygdomme, Viborg Regional Hospital at 8 A.M. in the overnight fasted state. A standard 18G venous catheter is inserted in a median cubital, basilic, or cephalic vein for blood sampling. Baseline and following, blood samples are drawn on the hour for 3 hours. Subsequently, participation is over, the catheter is removed with observation and compression 5-10 min. upon which the study participation is over for the part of the participants.

Ambulatory investigations (part 2)

Following the study day (part 1) participants are provided the full amount of either the ketone monoester drink or the comparator (placebo-drink). The drinks are provided in small plastic bottles

Methods

In order to obtain ketosis, participants ingest a common sports drink, KE4, which contains a ketone monoester. Upon this, ketosis is established with a substantial increase in BHB for estimation in the venous and whole blood, along with capillary measurements from the earlobe and finger pulp. The dosage will be 500 mg/kg for the study day (part 1) and daily, divided in two or three dosages as preferred, for the following 14 days (part 2)

Feasibility

No substantial practical challenges are expected – all equipment and competences are present in the Department of Internal Medicine and Department of Clinical Biochemistry. No recruitment issues are expected – this is a small-scale study with minimal impact in relation to participation.

The study is fully funded by independent research funds within departments involved although external funding will be sought for.

Analytic methods

BHB is estimated by the Ketosure™ for capillary measurements (finger pulp and earlobe), for venous blood samples, and HLCMS for full blood estimation of BHB as the reference standard.

Statistical considerations

Analytical approach

Following a visual examination of the graphical representation for linearity, differences are calculated using the paired t-test, agreement is determined using the Bland-Altman plot, and Pearson's r is used to determine correlations. Supporting calculations are performed using Lin's concordance correlation coefficient of absolute agreement. When comparisons over observations from part 1 and 2 are performed an repeated measurements anova equivalent analysis is applied.

Sample size and power calculation

No previous studies with data on BHB agreement have been performed. Based on our incidental findings, only very few subjects would be needed. The data is, however, far too small to base sample size calculations on.

Based on Boyd et al.[1] with highly correlated estimates of glucose and the acceptance of a type 1 error (α) of 0.05, type 2 error of 20% (β), a sample size of 13 participants is required to provide adequate statistical power to detect a difference of 0.58 mM in glucose estimates between capillary and venous blood samples with the standard deviation of 0.68 mM. Others have similarly found a clinically meaningful difference of 1 mM between sampling sites[8]. With α and β set as mentioned, a sample size of 20 participants is

required to provide adequate statistical power to detect a difference of 1 mM (SD = 1.5), should such a difference exist.

As such, we find it reasonable to include 15 patients in our study resulting in a power of 91% if expecting a meaningful difference of 1 mM and an average standard deviation of the two studies mentioned of 1.1 mM. Similar number of participants have been used elsewhere with regards to part 2 of this project and sample size as suggested is fully justified to test hypotheses of part 2.

Participants

Recruitment

Subjects will be recruited through notices on specific websites (sundhed.dk, forsøgsperson.dk) and social media (Facebook) along with board notice on selected local educational institutions, hospitals, and in newspapers.

First contact will be by telephone with the primary investigator(s) followed by the formal information on study participation (see section on recruitment and informed consent)

Inclusion criteria

Age 18-60 years

BMI 19-30 kg/m²

Expected ease of catheter insertion

Considered of sound health

Oral and written informed consent

Exclusion criteria

Inability to fully understand the consent including consent forms

Inability to cooperate to the study

Any electrolyte disorders, kidney disease or otherwise compromised renal function including excess risk hereof, e.g. hypertension, albuminuria, autoimmune disease, family history of kidney disease

Any liver or bile disease, or an increased risk of getting one, such as from hepatotoxic drugs, alcoholism, gallstones, pancreatitis, an autoimmune disease, or a history of liver disease in the family.

Diabetes mellitus or any metabolic and/or hormonal disease including diagnosed/undiagnosed reactive hypoglycemia or similar disorders. This includes treatment with drugs, and dietary supplements with inference on key metabolic or hormonal markers, e.g. insulin, glucagon, lipids, and GLP-1

Any use of illegal or otherwise use of medicinal products without prescription

Anemia or other known disease of the hematopoietic system

Previous bariatric surgery

Previous myocardial infarction or uncontrolled myocardial ischemia

Recent intended/unintended weight loss

Allergies to catheters or adhesives

Safeguards to minimize pain, discomfort, fear and other risks

Short-term and long-term risks and side effects

There are neither short-term nor long-term serious hazards or adverse effects to concern.

KE4 is a bitter sports drink that can cause moderate, temporary nausea and bloating.

Appetite may be slightly reduced over the full study period (part 2). Compared to sweet, salty, or umami-flavored beverages, the digestive adverse effects are equivalent to those of bitter-flavored beverages in general. This is a well-known side effect of bitter-tasting beverages in certain individuals.

As with the pricking of the fingers and earlobes, there is a small risk of infection following catheter placement, as well as a slight degree of discomfort.

Risk of radioactive radiation

There is no radiation involved in this study

Collection of new biological material

What and how much material

A total of 150 mL of blood is drawn in this study. This includes unavoidable spill from repeated sampling from indwelling catheter in part 1. No spillage is associated with part 2 since blood sampling is performed only twice in an outpatient setting (at the hospital laboratory for blood sampling)

Purpose

For analysis in bulk.

How long and what is the purpose of storage

All biological samples are stored for the full period of data collection and 18 months after in order to analyse all samples in bulk. Samples are stored at -80 °C.

Biobank

A research biobank is developed for the bulk analysis of all samples not analyzed on the day of the study, i.e. measurements using the Ketosure™ POCT device. The analyses are conducted within a few months at the earliest opportunity and surplus material is preserved as a biobank for future yet undetermined research.

Information from patient records

Access to participants' electronic patient records (exclusively and limited to solely laboratory results section) is included in study participation consent and necessary for practical reasons, i.e., information on medication, blood pressure readings. Only information otherwise routinely obtained as part of participants' treatment and are registered with the purpose of analysis within the frame of the study. Any information for use in the study given prior to oral and written consent are forwarded to the investigator.

Consent gives the study investigators as well as any control authority direct access to obtain information in the patient's health records, etc., including electronic health records, in order to see information about the participant's health conditions necessary for the implementation of the research project and for the purposes of any and all controls, including self-monitoring, quality control, and monitoring, which these are required to perform.

Handling of personal data in the study

The study is reported to and registered within Region Midt's research projects registration. The Data Protection Act is upheld in accordance with The General Data Protection Regulation in all aspects of the study.

All data are pseudonymized by de-identification when entered in data analysis sheet. A copy of the de-identification code kept only by primary investigator.

Access to data is equally open only to investigators until final analysis. Hereafter other investigators have access by which time all data are completely anonymized. After publication all data are open to public scrutiny.

Financial information

The study is initiated by primary investigator [name]

The study is financed from independent research funds within the Department of Internal Medicine, Regional Hospital Viborg. Additional external funding will be sought. All funding will be related to study expenses only, excluding any investigator salary which is cared for according to individual agreements with respective employers. All financial transactions are administered according to the research practices of the Central Denmark Region and Regional Hospital Viborg.

Research investigators and collaborators have no financial interests in the study.

Remuneration and/or other benefits to participants

Participants will be offered an inconvenience allowance of DKK 750 for completed study day participation (part 1) and DKK 750 for participation in part 2 (outpatient), thus DKK 1500 in total, with proportionate remuneration in the event of premature withdrawal. Requirements of the Committee Law §20, stk. 1, nr. 3 are upheld.

Recruitment of participants and informed consent

Potential participants are recruited through post on social media (Facebook and Twitter).

The first formal contact will be by telephone with the primary investigators ([name] or [name]) who are contacted by potential participant through notice of the study. Following this, the mandatory information about study participation, the interview, and the examination will be conducted as either a face-to-face meeting conducted with regard to privacy or as a video call, per request of the potential study participant. Potential study participants are informed that they are allowed to bring a companion to the interview.

Potential participants are always approached in a friendly and professional manner with a focus on minimizing any coercion.

After receiving information about study background and participation, potential participants are given reasonable time (one to two weeks or as deemed necessary by potential participant) to consider participation and allowing for further questions. Hereafter, they submit the signed consent form and give their oral consent.

It is emphasized to the potential participants that participation can be halted or stopped at any time upon request. Participants are not obliged to give the reason(s) for withdrawing consent and/or participation.

Special consideration will also be on ensuring that potential participants fully understand the study procedures.

Dissemination of results

The aim is to publish results, be them 'negative', 'positive' or inconclusive, in an internationally recognised peer-reviewed medical journal. If not accepted for publication, results are disseminated through the registration at clinicaltrials.gov where the study will be registered.

Ethics

Participation is associated with minute risks and discomfort and obtaining blood samples are done on routine visits to outpatient clinic as already planned. Hence, the study is believed to be justified with obtaining novel knowledge to better treatment options for future patients.

Information about the compensation scheme

The study is covered by the Danish Compensation Association

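### Part 1 takes three or four BHB pairs per participant, but the agreement methods named are for one pair each and the unit of analysis is not stated; pooling the pairs would usually overstate precision

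*Combined protocol and SAP*

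**What the plan says.** The Analytical approach section (Statistical considerations) assigns the Part 1 analyses as follows: "differences are calculated using the paired t-test, agreement is determined using the Bland-Altman plot". Correlation is by Pearson's r, and Lin's concordance coefficient is supportive. No repeated-measures version of any of these is named.

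The study-day section reads: "Baseline and following, blood samples are drawn on the hour for 3 hours". That is four draws. The Design section instead describes three exposures on a single day. Neither section timetables the finger and earlobe readings.

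One sentence does deal with repeated data: "When comparisons over observations from part 1 and 2 are performed an repeated measurements anova equivalent analysis is applied". Its scope is comparisons across the two parts, not agreement within the study day.

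The first Part 1 aim includes whether capillary-venous agreement depends on BHB level. The sample-size section works with one difference per participant.

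**The concern.** In their ordinary form, all four named methods treat pairs as independent. Pairs from one person on one morning probably are not. The Background itself gives haematocrit as the most prevalent explanation of capillary-venous differences in glucose, and a person's haematocrit should change little over three hours. If such a factor shifts a participant's differences in the same direction at every draw, 60 pairs carry less information than 60 independent ones.

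Agreement is the main goal of Part 1 and is meant to show whether a particular sampling site should be chosen for patients and research. A site difference declared too readily, or limits of agreement reported with false precision, would feed straight into that conclusion.

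**Working it through.** **1. The plan's own figures.** Inputs from the sample-size section: "acceptance of a type 1 error (α) of 0.05, type 2 error of 20% (β"), then "a sample size of 13 participants is required to provide adequate statistical power to detect a difference of 0.58 mM in glucose estimates" "with the standard deviation of 0.68 mM", and 20 participants "required to provide adequate statistical power to detect a difference of 1 mM (SD = 1.5), should such a difference exist". Sidedness is not stated; a two-sided paired t-test (noncentral t, noncentrality = difference/SD × √n) reproduces them:

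- 0.58/0.68 × √13 = 3.08: power 80.6% (12 participants give 76.7%).
- 1/1.5 × √20 = 2.98: power 80.7% (19 give 78.5%).
- 1/1.1 × √15 = 3.52: power 90.5%. With the unrounded mean SD, (0.68 + 1.5)/2 = 1.09, power is 91.0%, the stated value.

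These calculations rest on 15 independent differences, one per person.

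**2. Number of pairs.** 15 × 3 = 45 (Design section) or 15 × 4 = 60 (study-day section) per site comparison.

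**3. Standard error of the bias under pooling.** Let m be pairs per person, N = 15m, and ρ the intraclass correlation (ICC) of the differences. The documents give no ρ, so 0.1 to 0.5 is assumed. With constant bias:

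- true variance of the mean = σ²[1 + (m − 1)ρ]/N
- expected pooled s² = σ²[1 − (m − 1)ρ/(N − 1)]

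At ρ = 0.3 and m = 4, the pooled SE divided by the true SE is √[(1 − 0.9/59)/1.9] = 0.72. At m = 3 it is √[(1 − 0.6/44)/1.6] = 0.79.

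**4. Error rates.** Simulation with 15 people, normal differences, exchangeable correlation and no true bias. The interval on a limit of agreement uses SE = s√[1/N + 1.96²/(2(N − 1))].

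| Pairs | ICC | Pooled SE / true SE | Type I error, nominal 5% | Coverage of nominal 95% CI on a limit |
|---|---|---|---|---|
| 3 | 0.1 | 0.91 | 7% | 94% |
| 3 | 0.3 | 0.79 | 12% | 91% |
| 3 | 0.5 | 0.70 | 17% | 87% |
| 4 | 0.1 | 0.88 | 8 to 9% | 93% |
| 4 | 0.3 | 0.72 | 16% | 89% |
| 4 | 0.5 | 0.62 | 22% | 83% |

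A t-test on participant means held about 5% throughout. The pooled SD itself is only 0.2 to 1.3% low over this range, so the limits are nearly right; it is their precision that is overstated.

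**5. Bias that varies over the day.** With four draws and a bias of 0, 1, 2, 1 SDs of the difference, the pooled test of the average bias has type I error of 4, 8 and 13% at ICC 0.1, 0.3 and 0.5. With 0, 2, 3, 2 SDs it is 1, 3 and 6%. Both profiles are assumptions. Variation in bias inflates the pooled SD, which can offset or reverse the error.

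**6. The other two readings of the plan.**

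- *A separate test at each time.* Three comparisons at four times make 12 tests, and 1 − 0.95¹² = 46% if they are independent. With three times, 1 − 0.95⁹ = 37%. Correlated tests give less, so 46% is an upper-end figure. No adjustment is planned.
- *Averaging within participant.* The t-test is valid, but the SD of averaged differences is √{[1 + (m − 1)ρ]/m} of the single-reading SD. At ρ = 0.3 this is √(1.6/3) = 0.73 or √(1.9/4) = 0.69, so limits built on averages are about 30% too narrow for a single reading.

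**The case against.** The strongest reply is that the plan never says the pairs will be pooled. Its sample size uses one difference per participant, which suggests that the t-test was conceived with 15 units. A test on participant means, or at one time point, would not understate the standard error of the bias. The plan also promises only a Bland-Altman plot, without intervals on the limits, so the coverage figures concern something a careful analyst would add rather than something planned. Both the ICC and the constant bias are assumptions.

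Much of this stands. A reader might infer that the reported errors are certain to be too small; the documents do not support that, because pooling is unstated and step 5 shows that the direction can change. A reader might also infer that the 91% power is wrong; it is not, since it never counts repeated pairs. Nor can 60 pairs be taken as fact while the Design section says three exposures.

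What does not stand is that the plan is therefore adequate. Aim (i) asks about dependence on BHB level, and that level is varied mainly within each participant's day, so the aim calls for pairs from several times. The plan gives no way of combining them, and both alternatives to pooling have their own defect (step 6).

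**Conclusion.** The concern holds in a conditional form. The text establishes that there are several pairs per participant, that only methods for independent pairs are named for agreement, and that the repeated-measures sentence does not reach this analysis. The consequence depends on three assumptions: that pairs are pooled, that differences correlate positively within person, and that bias is roughly constant over the day. Under these, with an ICC of 0.1 to 0.5, a nominal 5% test rejects about 7 to 17% of the time with three pairs or 8 to 22% with four. Any nominal 95% interval on a limit covers about 94 to 87%, or 93 to 83%. The estimated limits are close to correct in that setting. If bias changes strongly with BHB, the pooled analysis mixes level effects with random error and its error rate may fall below nominal, which is a further reason to model level explicitly.

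**What to change.** - State the number of pairs per participant for each comparison, reconciling the three exposures with the four draws and giving the times of the capillary readings. State the unit of analysis.
- Replace the paired t-test and plain Bland-Altman analysis with a linear mixed model of the paired difference: random intercept for participant, and BHB level or time as fixed effect. BHB level answers aim (i) directly.
- Take limits of agreement from between- plus within-participant variance, allowed to vary with BHB level, with confidence intervals from a participant-level bootstrap or equivalent.
- Use repeated-measures versions of the correlation and of Lin's coefficient.
- Apply this to the comparisons already in the aims: capillary-venous, finger-earlobe, and venous point-of-care against HLCMS.

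The cost is revised analysis wording, a few lines of code and somewhat wider intervals. No further participants or samples are needed.

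### The 91% power quoted for 15 participants pairs the larger of two differences with an averaged SD; on the two source scenarios themselves the power is 87% and 67%

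*Combined protocol and SAP*

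**What the plan says.** All of the following is in the combined protocol and SAP, under Statistical considerations.

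- The Analytical approach section names the test: "differences are calculated using the paired t-test".
- Sample size and power calculation finds the available BHB data too sparse and uses published glucose data instead. Alpha is 0.05. The first scenario reads "type 2 error of 20% (β), a sample size of 13 participants is required to provide adequate statistical power", the aim being "to detect a difference of 0.58 mM in glucose estimates between capillary and venous blood samples with the standard deviation of 0.68 mM".
- The second scenario, with the same error rates, says that 20 participants are "required to provide adequate statistical power to detect a difference of 1 mM (SD = 1.5"). The plan treats 1 mM as a clinically meaningful difference between sampling sites.
- The plan then settles on 15, "resulting in a power of 91% if expecting a meaningful difference of 1 mM and an average standard deviation of the two studies mentioned", and gives that average as 1.1 mM.

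No other power figure is given for the chosen size. The section does not explain why the SDs are averaged while the difference is not, and it does not remark that 15 is below 20.

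**The concern.** Consecutive sentences say that 20 participants are required to detect 1 mM and that 15 detect 1 mM with 91% power. Only the SD has changed between them, from 1.5 to 1.1. One would expect a compromise between two sources to fall between them. Here the standardised effect is more favourable than in either source, because only one of the two inputs was averaged.

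The capillary-venous comparison is the first aim of part 1. If its result is not significant, a reader who relies on 91% power may conclude that the sampling sites are interchangeable. Under the less favourable of the plan's own scenarios the type 2 error is about 33%, against the 20% that the plan accepts.

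**Working it through.** **Inputs**, all from Statistical considerations: alpha 0.05; target power 80%; paired t-test; scenario A 0.58 mM, SD 0.68, 13 required; scenario B 1 mM, SD 1.5, 20 required; planned n = 15; stated power 91% at 1 mM, SD 1.1.

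**Assumptions**: alpha is two-sided, the SDs are those of the paired differences, and there is no dropout. The plan states none of these. The first two together reproduce all of its figures; a one-sided test, a normal approximation or a two-sample formula does not.

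**Formula**: power is taken from the noncentral t distribution with n − 1 degrees of freedom and noncentrality (difference / SD) × √n, at the two-sided 5% critical value.

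**Step 1: reproduce the plan's figures.**

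- Scenario A: n = 12 gives 76.7% and n = 13 gives 80.6%, so 13 is required. Agrees.
- Scenario B: n = 19 gives 78.5% and n = 20 gives 80.7%, so 20 is required. Agrees.
- Averaged SD: (0.68 + 1.5) / 2 = 1.09, printed as 1.1. With n = 15 the noncentrality is (1 / 1.1) × √15 = 3.52 and power is 90.5%; with the unrounded 1.09 it is 91.0%. Agrees.

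**Step 2: apply the same method, with n = 15, to each source scenario.**

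- A: (0.58 / 0.68) × √15 = 3.30; power 86.7%.
- B: (1 / 1.5) × √15 = 2.58; power 67.1%.

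A simulation with 400,000 replicates per scenario gave 86.7% and 67.2%.

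**Step 3: why the mixed figure exceeds both.** The standardised effects are 0.58 / 0.68 = 0.85, 1 / 1.5 = 0.67 and, for the mix, 1 / 1.1 = 0.91.

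**Step 4: other ways to combine the sources, n = 15.**

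- Difference held at 1 mM, variances averaged: √((0.68² + 1.5²) / 2) = √((0.4624 + 2.25) / 2) = 1.16; power 87.1%.
- Both inputs averaged: (0.58 + 1) / 2 = 0.79 mM with SD 1.09; power 74.2%, and 17 participants would be needed for 80%. This is an illustration and not a scenario in the plan.

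**Step 5: hold 1 mM fixed and vary only the SD, n = 15.** Power is over 99.9% at SD 0.68, 90.5% at 1.1, 87.1% at 1.16, 80.3% at 1.28 and 67.1% at 1.5. The 80% target therefore holds up to an SD of about 1.28.

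**The case against.** The strongest defence is that the difference to be detected is a target while the SD is a nuisance parameter, so the two need not come from the same study. Fixing a meaningful difference and drawing the SD from several sources is a recognised approach. On that view 91% lies between 67% (SD 1.5) and over 99.9% (SD 0.68), and is not extreme. Averaging variances instead of SDs still gives 87%, above the target. Every figure is a glucose proxy for BHB, and agreement itself is to be judged by Bland-Altman, which none of these powers addresses.

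Much of this stands. It rules out several stronger readings that a reader might infer:

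- *That 91% is miscalculated.* It is not; it follows from the stated inputs, whether the SD is taken as 1.09 or 1.1.
- *That the shortfall is concealed.* The 20, with its difference and SD, is in the sentence just before, and the 91% is openly conditional on the averaged SD. What is missing is any comment on the gap.
- *That the study misses its required sample size outright.* The plan gives two requirements. The 13 for scenario A is met; only the 20 for scenario B is not.
- *That the 1 mM comes from the larger study.* The documents do not give the source studies' sizes; it is simply the larger of the two differences.

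The defence does not supply the missing reason for the average. If 1 mM is the target and the SD is uncertain between 0.68 and 1.5, one power at a mid-point leaves out the unfavourable end, where 15 participants fall short. That glucose is only a proxy is a further reason to show the range.

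**Conclusion.** The point holds as an issue of sample-size assumptions, of moderate severity. The only power offered for 15 participants is correct for its inputs. However, it rests on an unexplained mix whose standardised effect (0.91) exceeds that of either source (0.85 and 0.67). On the plan's own scenarios the power is 87% and 67%: one meets the 80% target, and the other misses it by about 13 percentage points. These figures rest on the assumptions listed with the inputs; any dropout would lower them. The documents do not support calling this an arithmetic error or saying that 15 is too few in every scenario.

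**What to change.** Keep 15 participants and replace the 91% sentence with:

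> Based on glucose data, as a proxy for BHB, 15 participants give a two-sided paired t-test at alpha 0.05 a power of 87% for 0.58 mM (SD 0.68) and 67% for 1 mM (SD 1.5); the 80% target is not met in the second scenario.

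If a combined SD is kept, average the variances (SD 1.16, power 87% for 1 mM), give the reason for combining, and present it only as an intermediate case beside the 67%. Equal weighting of the two variances is itself an assumption, because the source studies' sizes are not given.

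The cost is one sentence and a less favourable stated power. No participants, procedures or analyses are added.
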